### *3.2.5 Pharmacokinetic Population*

The PK Population is defined as all randomized subjects who received at least one dose of study drug and have at least one evaluable PK sample. Subjects with major protocol deviation such as PK deviation or compliance issues may be excluded from the PK analyses (i.e. descriptive statistics) upon agreement with the Sponsor on case by case basis but all data will be listed. Values that are excluded from the analysis will be footnoted appropriately.

### *3.2.6 Pharmacodynamic Population*

The PD Population is defined as all randomized subjects who received at least one dose of study drug and have at least one evaluable PD sample.

## **3.3 Subject Data and Study Conduct**

### *3.3.1 Subject Disposition*

The number and percent of subjects who were screened, screen failed (by reason), completed Week 12, who completed the Open-Label Extension, withdrew early from the study, along with the reasons for withdrawal, will be presented by treatment group.

### *3.3.2 Protocol Deviations*

Major protocol deviations, i.e., those pertaining to GCP violations and those that may majorly affect the efficacy or safety evaluation, will be captured in the Study Management System as CSR Reportable deviations. These major deviations will be listed and summarized by category. These deviations will be reviewed prior to database lock to determine the potential impact on the interpretation of the efficacy and safety outcomes. The effect of any major protocol deviations and compliance will be assessed by conducting per-protocol analyses for the primary efficacy endpoint excluding subjects and/or study visits with major protocol deviations. This will be determined and documented prior to unblinding the study.

### *3.3.3 Analysis Populations*

Counts and percentages of subjects in each analysis population will be summarized by treatment group and in total based on all randomized subjects. Reasons for exclusion from each analysis population will also be summarized.

### *3.3.4 Demographic and Baseline Characteristics*

All subject baseline characteristics and demographic data (age, sex, race, ethnicity, weight, height, body mass index), viral test results, FSGS duration (from time of first diagnosis based on renal

biopsy), eGFR, proteinuria (UPCR), level of proteinuria (UPCR <3.5 vs UPCR  $\geq$ 3.5 g/g), proteinuria (UACR), prior Glucocorticoids or Immunosuppressant treatment, Calcineurin Inhibitor treatment (Cyclosporine, Tacrolimus), and diagnosis of nephrotic syndrome (defined as UPCR  $\geq$ 3.5 g/g) will be listed and summarized by treatment group and in total based on all randomized subjects.

### 3.3.5 Medical History

Medical history will be coded to system organ class and preferred term using the Medical Dictionary for Regulatory Activities (MedDRA) Version 20.1. Counts and percentages of subjects with medical history by system organ class and preferred term will be summarized by treatment and in total based on all randomized subjects.

### 3.3.6 Concomitant Medications

Concomitant medications will be coded using the World Health Organization (WHO) Drug Dictionary (September 2016E B2). Prior medications are defined as any medication taken prior to the first dose of study medication (within 12 weeks of screening). Concomitant medications are defined as any medication taken on or after the first dose of study medication. A medication can be classified as both prior and concomitant if it started before or during the screening period and continued into the treatment period. All prior and concomitant medications will be listed and summarized by Anatomic Therapeutic Chemistry (ATC) classification. All B-cell depleting antibodies, glucocorticoids and immunosuppressants taken within 6 months prior to screening may be summarized separately.

### 3.3.7 Study Drug Exposure and Compliance

Duration of exposure to study drug will be calculated as (date of last dose – date of first dose + 1). If date of last dose is not available, the date of discontinuation from study will be used. Duration of exposure to study medication will be summarized with descriptive statistics for double-blind period, open-label period and both periods. Exposure data will be provided for the following intervals, defined to align with the efficacy endpoints:

- $\leq$ 4 weeks (days 1-29)
- $>$ 4 and  $\leq$ 12 weeks (days 30-85)
- $>$ 12 and  $\leq$ 24 weeks (day 86-169)
- $>$ 24 weeks (days  $>$ 169)

Percent compliance to study drug will be summarized for double-blind period, open-label period and both periods, calculated as follows:

$$\text{Percent Compliance} = 100 \times \text{number of capsules taken} / (6 \times \text{number of days in the specified period}).$$

Percent compliance to the study drug regimen will be summarized by treatment group based on the Safety Population using counts and percentages of subjects with compliance in the following categories:

- <80%
- 80-120%
- >120%

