- The AIDS Clinical Trials Group Brief Peripheral Neuropathy Screening Tool Brief Peripheral Neuropathy Screening Tool (ACTG-BPNST) to assess early evidence of neuropathy;
- Monitoring for adverse events of infection;
- Alkaline phosphatase, ALT, AST and bilirubin (**total and direct**); to assess for evidence of drug induced liver injury.

For assessment of pharmacokinetics, study procedures will include

- Seven blood samples collected over 6 hours on Study Day 1 and at steady state (Study Day 15, or within 2 weeks thereafter) to assess AUC_{0-6} following the first administration of study drug, and at steady state;
- Assessment of C_{min} at intervals to ensure that exposure is within the projected range, with adequate safety margin based on the NOAEL established in preclinical toxicology;
- Upon discontinuation of treatment for any reason, collection of blood at 2 days, 7 days and 14 days following discontinuation to assess elimination.

All study procedures are presented in the [Time and Events table](#).

Subjects who are using an angiotensin converting enzyme (ACE) inhibitor, angiotensin receptor blocker (ARB) or other blocker of the renin angiotensin aldosterone system (RAAS), or who are using glucocorticoids, a calcineurin inhibitor or other immunomodulatory or immunosuppressive

[figure not shown]
therapy, should be on a stable dose for at least 4 weeks prior to screening. The dose of these medications must be kept constant over the course of the study in order to prevent undue influence of changes in these medications on the efficacy and safety assessments except when adjustment is required for patient well-being. The investigator must also attempt to keep doses of other medications, and lipid-lowering medications fixed throughout the blinded study period in order to prevent undue influence of changes in these medications on the efficacy and safety assessments.

Subjects who experience deteriorating renal function based on an increase in serum creatinine of at least 50% (confirmed by a repeat measurement after 2 weeks) which is otherwise not explained (e.g., dehydration, new medication), or increase in UPCR of >3.0 g/g (confirmed by a repeat measurement after 2 weeks) during the 12-week treatment period, will exit the treatment phase of the study and be treated at the discretion of the treating physician. All subjects who discontinue treatment will remain in the study for follow up and outcome recording.

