| Anemia | Hemoglobin reduced from baseline by ≥ 2 g/dL and deemed clinically significant by the PI | Halt treatment then reassess after 2 weeks | If normal, continue to treat at reduced dose, defined as next lower dose. Otherwise, contact Medical Monitor to discuss next steps |
| Reticulocyte Count | Increase from baseline in reticulocyte count by ≥ 2 units (% of RBC) that is not otherwise explained | Halt treatment then reassess after 2 weeks | If within normal range for the hematocrit, continue to treat at reduced dose, defined as next lower dose. Otherwise, contact Medical Monitor to discuss next steps |

| Assessment | Event | Timing | Response |
|-------------------------------------|---|--|---|
| Peripheral Neuropathy | ≥ moderate symptoms limiting (limiting instrumental activities of daily living) or asymptomatic (based on diagnostic evaluation only) and deemed clinically significant by the PI | Halt treatment then reassess after 2 weeks | Contact Medical Monitor to discuss next steps |
| Other Clinically Significant Events | Any adverse events assessed as moderate, related to study drug, and clinically significant | Halt treatment then reassess after 2 weeks | Contact Medical Monitor to discuss next steps |

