5.5. Removal of Subjects from Therapy of Assessment

Investigators must clearly distinguish between study drug treatment discontinuation and study withdrawal. Subjects who discontinue study drug treatment or who initiate medication changes (including those prohibited by the protocol) will not be automatically withdrawn from the study, but all efforts must be made to continue to follow the subjects for all regularly scheduled visits. The Medical Monitor should be contacted to determine how to address the specific situation.

Investigators must take appropriate measures to make sure that subjects are motivated to comply with all requirements of the protocol in order to minimize the amount of missing data. Subjects who discontinue study treatment early or initiate medication changes (including those prohibited by the protocol) should continue to be followed for all regularly scheduled visits for safety and efficacy assessments. Investigators and their staff must take measures to actively maintain contact with their subjects in the study, such as telephone calls, texts, or emails between visits, and offers for transportation support to visit the study site.

5.5.1. Subjects may be withdrawn from the study for the following reasons:

1. Subject withdrawal of consent to contribute additional outcome information;
2. Subject non-compliance with dosing or diary completion;
3. Loss to follow-up;
4. Sponsor's decision to terminate the study.

5.5.2. Subjects may discontinue study drug treatment for any of the following reasons:

1. Subject withdrawal of consent;
2. The Investigator may discontinue study drug treatment if, in his/her clinical judgment, it is in the best interest of the subject;
3. The Sponsor may request discontinuation of study drug treatment for safety reasons or non-compliance with treatment;
4. The Sponsor may request discontinuation of study drug treatment due to new or increased glucocorticoid/immunosuppressant treatment.

In the event of early withdrawal from the study, the tests and evaluations listed for the Early Termination visit in [Section 7.14](#) will be performed, whenever possible. Data collected at this visit will be designated as an "Early Termination" visit in the EDC. The Sponsor should be notified of all study drug treatment and study withdrawals in a timely manner.

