7.14. Early Termination Visit (See Section 7.14 for PK elimination guidelines)

If a subject will be withdrawn early from the study, the following termination procedures should be completed whenever possible:

- **Whenever possible, the subject will be asked to collect all urine for the 24 hours after the last dose of study drug.**

- An abbreviated, symptom-directed physical examination
- Vital signs (weight, temperature, blood pressure, heart rate) after at least 3 minutes of rest
- Blood samples and urine will be collected for shipment to the central laboratory for serum chemistry, hematology, serum pregnancy test (in women of childbearing potential) and quantitative urinalysis
- Need for dialysis will be recorded
- **If available, process the first morning void urine sample collection for UPCR and UACR assessment**
- **If available, process the 24-hour urine sample for quantitative urinalysis, UPCR, UACR, Cystatin C, Urine MCP-1, MCP-1/creatinine ratio urine PD assessment and urine protein excretion/day**
- 12 Lead ECG after at least 3 minutes of rest, will be recorded and assessed for any clinically significant abnormality
- Drug accountability and reconciliation with subject completed diaries
- Any changes in concomitant medication use, including plasma therapy regimen, will be recorded
- Any adverse events will be recorded. If an adverse event remains unresolved at the conclusion of the study, a clinical assessment will be made by the Investigator and the Sponsor's Medical Monitor to determine whether continued follow-up of the adverse event is warranted
- A final safety follow-up visit will be scheduled for 4 weeks after subject discontinues study drug

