9.3.4. Study Drug Exposure and Compliance

Subject drug exposure will be calculated based on the study drug dispensing and return records, as well as CCX140 plasma concentrations over the course of the study. The CCX140-B/placebo compliance will be calculated comparing the study drug dispensed and the study drug returned. The study drug exposure (duration, total dose, and average daily dose) and compliance will be listed and summarized.

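### A missing last-dose date is filled with the study-discontinuation date, which can count off-drug follow-up as exposure, and the SAP leaves out total and average daily dose without declaring it

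*SAP*

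**What the plan says.** SAP 3.3.7 gives one formula for exposure: "Duration of exposure to study drug will be calculated as (date of last dose – date of first dose + 1", closing the bracket there. Its fallback is: "If date of last dose is not available, the date of discontinuation from study will be used". Duration is then summarised for the blinded period, the open-label period and both together, and in four intervals with cut points at 4, 12 and 24 weeks. The same section defines compliance as units taken divided by six per day in the period, in the categories below 80%, 80-120% and above 120%.

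The protocol keeps the two stopping events apart. Section 5.5: "Investigators must clearly distinguish between study drug treatment discontinuation and study withdrawal". The same section says that subjects who stop treatment early "should continue to be followed for all regularly scheduled visits for safety and efficacy assessments". Section 4: "All subjects who discontinue treatment will remain in the study for follow up and outcome recording". Even for early termination, Section 7.14 adds: "A final safety follow-up visit will be scheduled for 4 weeks after subject discontinues study drug".

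On what to report, protocol 9.3.4 states: "The study drug exposure (duration, total dose, and average daily dose) and compliance will be listed and summarized". The SAP mentions neither total dose nor average daily dose. SAP Section 6, which lists departures from the protocol, names only the responder analysis and MCP-Mod. SAP Section 1 says that the SAP takes precedence.

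The protocol also provides for interrupted and lowered dosing. For several events Table 2 says "Halt treatment then reassess after 2 weeks", in some cases followed by resumption at the next lower dose. Section 4.2 allows the DMC to recommend stepping an arm down.

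**The concern.** Two gaps meet in one section.

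First, the fallback treats leaving the study as if it were the last dose. Under this protocol a subject who stops drug normally stays on for visits, so the substituted date tends to be an off-drug date. The error has one direction, and it can move a subject into a longer exposure interval than the one the subject belongs in.

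Second, duration alone cannot tell a subject dosed without a break from one who was held for two weeks and resumed at a lower dose. The protocol's own measures, total and average daily dose, would show the difference, but the SAP is silent on them.

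At stake is the description of how much drug each arm received in a dose-ranging trial that has safety and tolerability as a primary objective. Arms are planned at 10 subjects, so one misdated subject is visible in an arm summary.

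**Working it through.** The plan gives no figure to reproduce. The check applies the SAP formulas to assumed dosing histories. Every stop, hold, reduction and exit day below is an assumption.

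**Inputs.** Blinded dosing lasts 84 days and total treatment 168 days (protocol Section 4). The safety visit is 4 weeks after stopping (7.14). The Week 16 and Week 28 visits fall on Days 113 and 198 (Time and Events Table; Sections 7.9 and 7.12 give 114 and 197, a one-day difference). Daily doses are 30 mg for 15 mg twice daily and 20 mg for 10 mg twice daily.

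**1. Missing-date fallback.** With first dose on Day 1, true duration is the day number of the last dose and recorded duration is the day number of study exit. Excess = exit day − last-dose day.

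| Last dose | Study exit | True days | Recorded days | Excess | SAP interval, true → recorded |
|---|---|---|---|---|---|
| Day 28 | Day 56 (4-week safety visit) | 28 | 56 | 28 | up to 4 wk → 4-12 wk |
| Day 84 | Day 113 | 84 | 113 | 29 | 4-12 wk → 12-24 wk |
| Day 168 | Day 198 (study end taken as exit) | 168 | 198 | 30 | 12-24 wk → over 24 wk |
| Day 28 | Day 113 | 28 | 113 | 85 | up to 4 wk → 12-24 wk |
| Day 28 | Day 198 (extreme) | 28 | 198 | 170 | up to 4 wk → over 24 wk |

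In an arm of 10, one subject from the first row adds 28/10 = 2.8 days to the mean duration. One from the fourth row adds 85/10 = 8.5 days.

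**2. Holds and reductions, no missing date.** Take a subject on 15 mg twice daily with 28 days at full dose, a 14-day hold, and then 42 days at 10 mg twice daily.

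- SAP duration: 84 days, the same as for uninterrupted dosing.
- Total dose: 28 × 30 + 42 × 20 = 1680 mg, against 84 × 30 = 2520 mg uninterrupted.
- Average daily dose over 84 days: 1680/84 = 20 mg/day, against 2520/84 = 30 mg/day.

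**3. Does compliance show it?** Compliance = 100 × units taken / (6 × days in period), with 84 days in the period.

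- 14-day hold, six tablets on all other days: 100 × (6 × 70)/(6 × 84) = 83.3%, in the 80-120% category.
- 17-day hold: 100 × 67/84 = 79.8%, so holds of 17 days or more do drop below 80%.
- Step-down without a hold, still six blinded tablets daily (assumed): 100%.
- The history in step 2, if the reduced dose were taken as four tablets daily: 100 × (6 × 28 + 4 × 42)/(6 × 84) = 66.7%.

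Compliance therefore picks up long holds and some reductions, and misses short holds and any step-down that keeps the tablet count.

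**4. Choice of denominator.** For a 14-day hold with the same dose resumed, total dose is 30 × 70 = 2100 mg. Divided by all 84 days this is 25 mg/day, which shows the hold. Divided by the 70 dosed days it is 30 mg/day, which hides it.

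**The case against.** The strongest reply is that the fallback will rarely be used. Subjects complete a diary after each dose, tablets are counted, last-dose time is recorded before PK sampling at most on-treatment visits, and the 2-, 7- and 14-day elimination visits are timed from the last dose. A subject well followed off drug should have a known last-dose date. The fallback may mainly reach subjects lost to follow-up, where study exit could lie close to the last dose. This stands as a limit on frequency, which the documents do not give. It does not make the rule right when it is used.

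It can also be said that first-to-last-dose duration is a clear definition, that protocol 9.3.4 does not define duration net of holds, and that all data are listed by subject (SAP Section 7). This is fair. The duration formula is acceptable as duration. The gap is that the dose measures that go with it are missing from the summaries, and the raw information is not lost.

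A reader might infer more than the documents support:

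- *That exposure is commonly inflated several-fold.* The Day 28 to Day 198 case is extreme. Protocol 8.5 makes Week 16 the last visit for everyone outside the open-label extension.
- *That every subject's exposure is too long because of holds.* Only held subjects are affected.
- *That the error gathers in the highest-dose arm.* Nothing shows this. Treatment also stops for rising creatinine or UPCR, which could occur in any arm.
- *That adverse event rates or efficacy results are distorted.* SAP 3.6.1 reports counts and percentages, the MMRM uses treatment group, MCP-Mod uses assigned dose levels, and per-protocol status uses accountability-based compliance. None takes exposure duration as an input.

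**Conclusion.** The point holds as a reporting fault in SAP 3.3.7, with two parts.

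The fallback conflicts with the protocol's separation of stopping drug from leaving the study. If no drug is taken after study exit, it can only lengthen exposure: by about 28 to 30 days when exit is at the 4-week safety visit, and by more with longer follow-up. It has no stated limit at the end of a treatment period. It applies only to subjects with a missing last-dose date, in unknown number.

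The omission of total and average daily dose does not depend on missing dates. It is a departure from protocol 9.3.4 that Section 6 does not declare. Because of it, a subject who received two thirds of the planned milligrams (1680 of 2520 in the assumed case) has the same summarised duration as one who received all of them, and compliance reveals this only in part.

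The consequence is confined to descriptive exposure summaries behind the safety objective. It should be corrected, but it does not threaten the efficacy analyses or the adverse event percentages.

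**What to change.** Amend SAP 3.3.7 in two places.

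1. **Missing last-dose date.** Use the latest dosing date supported by the diary or tablet reconciliation. If there is none, use the recorded treatment-discontinuation date. The imputed date should never be later than treatment discontinuation, and should be capped at the end of each treatment period. Report how many dates were imputed, by arm.
2. **Dose measures.** Restore total dose (mg) and average daily dose by arm and period. Define average daily dose as total mg divided by all days from first to last dose in that period, with held days kept in the denominator so that holds and reductions show. If leaving these measures out is intended, declare it in Section 6.

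The cost is a few lines of SAP text and a small amount of programming. The inputs are diaries, tablet counts, dispensing and return records and discontinuation data that the protocol already collects. No visit, assessment or treatment rule changes.

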## 2.2 Study Design

### 2.2.1 Overview

This study will evaluate the efficacy, safety, tolerability, and pharmacokinetics of up to 12 weeks of treatment with each of three dose regimens of CCX140-B or placebo, when used in combination with stable standard of care therapy in subjects with FSGS with significant proteinuria, assessed as UPCR > 1g/g at Screening.

The target is to enroll 40 adult male or female subjects in this randomized, double-blind, placebo-controlled, Phase 2 study. Subjects will be randomized 1:1:1:1 to one of four treatment groups:

- Group A: Placebo (N=10)
- Group B: CCX140-B 5 mg once daily (N=10)
- Group C: CCX140-B 10 mg twice daily (N=10)
- Group D: CCX140-B 15 mg twice daily (N=10)

[figure not shown]
Subjects will be screened within a period not to exceed 28 days prior to Study Day 1 (the first day of dosing). All subjects will take blinded study medication in the morning and evening, with or without food, for 84 consecutive days. Following the 84-day blinded dosing period, all subjects will take open label CCX140-B for an additional 84 days at the highest dose under evaluation, currently planned to be 15 mg twice daily.

During the treatment period, eligible subjects will visit the study center on Study Days 1, 8, 15, 29 (Week 4), and Weeks 8, 12 (primary endpoint), 13, 16, 20, and 24 for study procedures including interval history, physical examination and vital signs, ECG, study questionnaires, and collection of blood and urine. Subjects will discontinue study drug as of Study Day 169 (Week 24) and will return for a follow up visit on Week 28. When feasible, upon discontinuation of treatment for any reason a sample of whole blood should be collected for assessment of elimination 2, 7 and 14 days after the final dose of CCX140-B (or placebo).

A study schema is depicted in Figure 1. All study procedures are presented in Table 1.

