### *2.2.3 Study Drug*

Study drug will be administered as 3 tablets twice daily (5 mg CCX140-B tablets, matched placebo, or combination) for up to 12 weeks in a double-blind manner.

CCX140-B will be administered as up to 3 tablets (5 mg each) twice daily during study weeks 13 through 24 in an open-label manner.

Study drug will be supplied to the study center in plastic bottles, each bottle containing 30 tablets.

During the blinded portion of the study, study drug will be supplied to the subject in kits, each kit containing 3 bottles labeled with a yellow band for use in the morning and 3 bottles labeled with a blue band for use in the evening. Each bottle will be also labeled with a distinguishing number. Subjects will be instructed to take one tablet from each of the three yellow bottles in the morning, and one tablet from each of the three blue bottles in the evening and to maintain a dosing diary.

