### *3.2.3 Per-Protocol (PP) Population*

The PP Population is defined as all subjects in the ITT Population who have  $\geq 80\%$  compliance with the study drug administration and do not have protocol deviations that could significantly affect the interpretation of the results for the primary endpoints. The PP Population will be a secondary population for analysis of the primary efficacy endpoint.

The following aspects will be considered for subjects to be excluded from the PP analysis:

- Subjects with significant protocol deviations regarding inclusion and exclusion criteria that may impact evaluation of the primary endpoints.
- Subjects with significant lack of compliance of study medication administration (CCX140-B /placebo) defined as: All subjects who were  $<80\%$  compliant with taking CCX140-B /placebo based on study medication accountability records.
- Subjects administered non-protocol allowed medications such as, calcineurin inhibitors, ACE-inhibitors or ARBs, spironolactone, eplerenone, antihypertensive, diuretics, immunosuppressants or calcineurin inhibitors or subjects with dose increases of such drugs during the course of the study.

Subjects to be excluded from the PP population will be identified and documented prior to the database lock and unblinding for analysis. A subject's data could be partially excluded from analysis depending on when the deviation occurred. For example, if a deviation occurred during the open-label extension (OLE) that did not impact the data from the double-blind period, only the data during the OLE will be excluded.

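### The SAP compliance formula assumes six tablets on every day of the period, so an adherent subject on a directed hold or a lower open-label tablet count is scored as under-compliant

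*SAP*

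**What the plan says.** - **Formula.** SAP 3.3.7 divides tablets taken (the section calls them capsules) by six times the "number of days in the specified period". It adds that "Percent compliance to study drug will be summarized for double-blind period, open-label period and both periods". Subjects in the Safety Population are then tabulated as below 80%, 80 to 120%, or above 120%.
- **Tablet count.** For the blinded phase SAP 2.2.3 says "Study drug will be administered as 3 tablets twice daily". For the open-label phase it says "CCX140-B will be administered as up to 3 tablets (5 mg each) twice daily during study weeks 13 through 24". Protocol 6.3.2 lets the open-label dose be lowered, and Protocol 6.1 describes the open-label bottles as all active.
- **Directed holds.** Protocol 4.2.1, Table 2, gives the instruction "Halt treatment then reassess after 2 weeks" for LDH, haemoglobin, reticulocyte, neuropathy and certain other adverse events. For the first three, treatment resumes at the next lower dose if the value has normalised; otherwise the Medical Monitor is contacted. For the last two, the Medical Monitor is contacted in every case.
- **PP rule.** SAP 3.2.3 lists as a ground for exclusion "Subjects with significant lack of compliance of study medication administration", meaning under 80% by accountability records. It does not cite 3.3.7 or say which period counts. It gives the example that an open-label deviation which left the double-blind data unaffected removes only the open-label data.
- **Protocol basis.** Protocol 6.7 judges compliance against the prescribed dose, and Protocol 9.3.4 compares drug dispensed with drug returned. SAP section 6 does not list the fixed six-a-day denominator as a change.

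**The concern.** A compliance measure should show how far subjects departed from their instructions. With a fixed denominator, a subject who stops when told to stop, or takes fewer tablets because fewer were prescribed, scores the same as one who forgets doses.

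Two things are at stake. The compliance table could show adherent subjects as non-compliant. And if the 80% rule for the PP set is read from this formula, membership could depend on events that may be drug toxicity, and so on dose. With 10 subjects per group, a few such exclusions would be visible in the PP results.

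**Working it through.** **Inputs**
- Six tablets a day in every blinded arm: 3 × 2 = 6 (SAP 2.2.3). The plan's factor is reproduced.
- Blinded phase: "for 84 consecutive days". Open-label phase: "for an additional 84 days at the highest dose under evaluation" (both SAP 2.2.1). Full denominators are 6 × 84 = 504 for each period and 6 × 168 = 1008 for both.
- PP cut-off 80% (SAP 3.2.3).
- Assumptions: the period means all its calendar days, and the 80% rule uses the 3.3.7 formula.

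**Double-blind period, hold of h days, otherwise fully adherent**

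Compliance = 100 × 6 × (84 − h) / (6 × 84)

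| Days held | 84-day period | 85-day period |
|---|---|---|
| 14 | 83.3% | 83.5% |
| 16 | 81.0% | 81.2% |
| 17 | 79.8% | 80.0% |
| 18 | 78.6% | 78.8% |
| 28 (two 14-day holds) | 66.7% | 67.1% |

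The break point is 0.20 × 84 = 16.8 days. The 85-day column is shown because the exposure intervals in SAP 3.3.7 count the first 12 weeks as days 1 to 85; a 17-day hold then just passes.

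After one 14-day hold, the adherence needed on the other 70 days is 0.80 × 84 / 70 = 96%. At 95% the score is 0.95 × 70 / 84 = 79.2%.

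A blinded step-down does not change the score if another arm's kit is used, because every arm takes six tablets a day.

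**Open-label period, fully adherent**
- Four tablets a day (10 mg twice daily) throughout: 4 × 84 / 504 = 66.7%.
- One tablet a day (5 mg once daily) throughout: 84 / 504 = 16.7%.
- One subject with 28 days at six, a 14-day hold, then 42 days at four: (168 + 168) / 504 = 66.7%.

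That a lower dose means fewer tablets is an inference from the all-active bottles; no placebo fill is described for this phase.

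**Both periods combined**
- Four a day in open label: (504 + 336) / 1008 = 83.3%.
- The same plus a 14-day blinded hold: (420 + 336) / 1008 = 75.0%.
- One a day in open label: (504 + 84) / 1008 = 58.3%.

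**Early stops.** If the blinded period is fixed at 84 days, a subject who stops after 67 dosing days scores 67 / 84 = 79.8%. If the period ends at the last dose, the same subject is not penalised. The SAP does not say which applies.

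**With tablets prescribed as the denominator.** A fully adherent subject scores 100% in each hold or reduced-dose case: 420 / 420 with a 14-day blinded hold, 336 / 336 at four a day in open label.

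**What lost subjects would cost.** The sample-size section's half-width is t(0.95, df) × 0.70 × √(1/n₁ + 1/n₂). At 10 versus 10 this gives 0.543, the plan's own figure. It becomes 0.580 at 10 versus 8 and 0.617 at 8 versus 8. The documents give no hold rate, so these show scale only.

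**The case against.** A reader might infer that any directed hold, or any lowered open-label dose, pushes subjects out of the PP set and biases the PP analysis of the primary endpoint. The documents do not support that.
- One 14-day hold scores 83.3% and passes. Failing needs a longer hold, a second one, or missed doses as well.
- The SAP's PP analysis of UPCR is confined to the double-blind period, and SAP 3.2.3 limits the loss from an open-label deviation to open-label data. Even if compliance over both periods decided membership, four tablets a day in open label alone would score 83.3%.
- No frequency, direction or size of bias can be derived.

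The other side has further points. SAP 3.5.1 assumes 15 mg twice daily for everyone in the open-label phase, which is six tablets, so the factor matches the plan. SAP 3.2.3 rests on accountability records, lists compliance among matters to be considered, and never cites 3.3.7. A prescribed-tablet denominator would also keep in the PP set a subject held for 28 of 84 days, with a third less exposure; whether PP should mean following instructions or receiving enough drug is partly the sponsor's choice.

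Most of this stands as a limit on the consequences. It does not rescue the formula. The same SAP calls the open-label dose a ceiling, Table 2 provides for individual reductions, and 3.3.7 is the only compliance formula in the SAP, with the same 80% cut. Two weeks is the point of reassessment, not a guaranteed restart, so longer holds are foreseeable.

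**Conclusion.** The point holds as a minor definitional fault. The denominator is wrong whenever fewer than six tablets a day are prescribed or treatment is halted on instruction.

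The clearest effect is in the open-label period: 66.7% for a fully adherent subject at four tablets a day, a below-80% entry in the compliance table, and possible loss of open-label data from PP analyses. SAP 3.4 runs efficacy endpoints in both ITT and PP, and SAP 3.4.2 allows PP denominators for Week 24 remission. This arises only if the dose is lowered, for everyone or for an individual; the documents report no such reduction.

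In the double-blind period the effect on PP membership is conditional on the holds shown above and on the inferred link between the 80% rule and the 3.3.7 formula. The primary ITT analysis is untouched, and a lowered open-label dose does not by itself remove anyone from the double-blind PP analysis of UPCR.

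**What to change.** - In SAP 3.3.7, define the denominator as tablets prescribed: the daily tablet count in force times days on treatment, excluding protocol-directed interruptions, derived from diaries and accountability records. State how early stops count.
- In SAP 3.2.3, cite that definition. State that double-blind compliance governs the double-blind PP set and open-label compliance governs open-label PP data, with the combined figure descriptive only.
- Report days held separately, as exposure.
- Replace capsules with tablets; this is clerical.

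The cost is one changed derivation and no change to any dosing rule. The documents name no data field for interruption dates, so the team should first confirm that directed holds can be identified from the diaries and tablet counts. The downside is small: a subject with a long directed hold stays in the PP set with less exposure, so show those subjects separately or in a sensitivity run. Settle this before database lock, because SAP 3.2.3 requires PP exclusions to be documented by then.
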